After a subject is able to abstain from substances for a period of 21+ days, they will have the option to complete a 3-night stay on the CNRU, where they will participate in imagery training and 3 laboratory sessions. After completion of the laboratory sessions, subjects will be discharged from the inpatient unit at least one day after the laboratory sessions.

Subjects will undergo the same titration onto study medication as outlined above. If the subject decides to complete the laboratory component, they will be maintained on 16.0mg dose of PRZ/PLA medication during the week of the inpatient laboratory sessions, after which they will undergo the above mentioned taper or continue to take their medication for 9 weeks in outpatient

treatment. In the event that someone continues to use alcohol while in the study, they may be asked to come in for more frequent appointments to assess for adverse symptomatology and meet with the study psychiatrist. Similar methods have been used in our outpatient lofexidine study and no adverse interaction events are anticipated.

Table 1: PRZ/PLA Dosing

	Prazosin PRZ (N = 75) (Male / Female)			Placebo (PLA) (N = 75) (Male / Female)		
Week 1	AM	PM	Evening	AM	PM	Evening
Days 1 -2 (1mg / 1mg)	0mg / 0mg	0mg / 0mg	1mg / 1mg	0mg / 0mg	0mg / 0mg	1mg / 1mg
Days 3 (2mg /1mg)	1mg / 0mg	0mg / 0mg	1mg / 1mg	1mg / 0mg	0mg / 0mg	1mg / 1mg
Days 4-6 (6 mg/4mg)	2mg/1mg	2mg/1 mg	2 mg/2mg	2mg/1mg	2mg/1 mg	2mg/2mg
Week 2						
Days 7-9 (10mg /8mg)	3mg / 2mg	3mg / 2mg	4mg /4mg	3mg / 2mg	3mg / 2mg	4mg /4mg
Days 10 – 13 (12mg/12mg)	4mg /4mg	4mg/4mg	4mg /4mg	4mg /4mg	4mg /4mg	4mg /4mg
Day 14 (16mg/16mg)	5mg/5mg	5mg/5mg	6mg/6mg	5mg/5mg	5mg/5mg	6mg/6mg

Follow-up:

Upon completion of outpatient treatment, follow-up interviews will be scheduled with all subjects. If a subject decides to complete only the inpatient phase, follow-up appointments will be scheduled after the inpatient phase is complete. Follow up interviews will be scheduled at 30 days. Urine monitoring, assessment of craving, cocaine abstinence symptoms, self report of drug use and stress and craving scales, will be assessed during the follow-up appointment.

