with medication and alcohol withdrawal/anxiety, we used a conservative effect size of $d = .60$ for detection of significant main effects and possible interactions in the clinical trial. At this effect size and power = .80, with $p < .05$, sample size estimates from Cohen (1988, p.258) indicated that we would require 25 subjects per cell to adequately assess the proposed hypotheses for the clinical trial (total $N = 100$). Including a 15-20% drop-out after enrollment, we estimated recruitment of 120 AD patients into the trial to ensure adequate power for the trial.

Data Analysis for Laboratory Study: Repeated measures ANOVA and mixed model procedures to assess treatment group differences in alcohol craving and stress related changes (heart rate, blood pressure, HPA and catecholamine responses) during laboratory exposure to stress and drug cues as compared to neutral imagery conditions. Non-parametric tests will be used to assess occurrence of side effects, treatment retention rates, alcohol use measures, CIWA scores and perceived stress scores during the outpatient treatment phase. The number and type of AE's for the two treatment groups will be conducted using t-tests, chi-square tests and ANOVAs as appropriate. Findings will be used to estimate effect sizes for the medication and guide the larger randomized clinical trial.

Data Analysis for the 12-week clinical trial Study: For this phase, the following moderator and primary and secondary outcomes are specified:

Primary Moderator Measure: Alcohol withdrawal symptoms, as measured by the CIWA alcohol withdrawal scale,

Primary Outcome Measures in the outpatient treatment phase: These are: (1) Heavy drinking days (5 or more for men, 4 or more for women) during the 12 week period, and (2) Any drinking days. Both will be assessed daily using smartphone or interactive voice recording surveys completed by the patients and also with weekly urine drug screens/breathalyzer reports and self report of drug use on the Substance Use Calendar.

Secondary Outcome Measures in the outpatient treatment phase: Secondary outcome measures will include alcohol craving scales, anxiety (Hamilton Anxiety Scale) and depression (CES-D) and sleep quality using the Pittsburgh Sleep Quality Index – PSQI).

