This aim will be tested using mixed model analysis of variance procedures for each of the following dependent measures: VAS alcohol craving scale; VAS anxiety scale; brief CCQ; DES emotions of anger, sadness and fear; heart rate, blood pressure and HPA measures of ACTH and cortisol and NE and EPI.

Specific Aim 2: To evaluate the efficacy of Prazosin versus Placebo in high alcohol withdrawal individuals on primary outcomes of: (a) heavy drinking days (HDD) over 12 week period; (b) Any drinking days (DD%).

Hypothesis 2: In high alcohol withdrawal individuals, Prazosin group will show significant reductions in HDD% and DD% during the 12 week treatment period as compared to Placebo group. No differences between medication treatment groups in the Low alcohol withdrawal individuals will be observed.

Secondary outcome measures such as alcohol craving, Anxiety, depression and sleep quality will be assessed. Findings PSS, COPE and LES scores will be examined.

SECTION VI: RESEARCH INVOLVING DRUGS, BIOLOGICS, RADIOTRACERS, PLACEBOS AND DEVICES
--

If this section (or one of its parts, A or B) is not applicable, state N/A and delete the rest of the section.

A. DRUGS, BIOLOGICS and RADIOTRACERS

1. **Identification of Drug, Biologic or Radiotracer:** What is (are) the **name(s)** of the drug(s) biologic(s) or radiotracer(s) being used? Identify whether FDA approval has been granted and for what indication(s).

Prazosin (marketed by Pfizer Inc) is an alpha-1-adrenergic agonist that is known to preferentially bind to post-synaptic alpha1-adrenergic receptors. Walker et al (2008) found that Prozaosin was effective in suppressing excessive alcohol consumption in rats, suggesting the involvement of the noradrenergic system in alcohol dependence. Simpson et al. (2007) found similar findings in a pilot trial using prozosin for treatment of alcohol dependent men and women. Prazosin therefore is an excellent candidate for treating alcohol seeking behaviors. It may also be more easily tolerated than those medications which directly modulate these transmissions.

All protocols which utilize a drug, biologic or radiotracer **not** approved by, but regulated by, the FDA, or a radiotracer regulated by the RDRC, must provide the following information:

- What is the Investigational New Drug (IND) **number** assigned by the FDA? N/A
- Who holds the IND?
- All protocols which utilize a radiotracer not approved by, but regulated by the FDA must provide the IND number: _____

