Yes If yes, describe the conditions under which continued access to study drug(s) may apply as well as conditions for termination of such access.

No If no, explain why this is acceptable.

B. DEVICES

1. Are there any investigational devices used or investigational procedures performed at YNHH, e.g., YNHH Operating Room or YNHH Heart and Vascular Center? Yes No

SECTION VII: RECRUITMENT/CONSENT AND ASSENT PROCEDURES

1. Targeted Enrollment: Give the number of subjects:

a. targeted for enrollment at Yale for this protocol
150 alcohol dependent men and women

b. If this is a multi-site study, give the total number of subjects targeted across all sites

N/A

2. Indicate recruitment methods below. Attach copies of any recruitment materials that will be used.

- | | | |
|---|--|---|
|  Flyers |  Internet/Web Postings |  Radio |
|  Posters |  Mass E-mail Solicitation |  Telephone |
|  Letter |  Departmental/Center Website |  Television |
|  Medical Record Review |  Departmental/Center Research Boards |  Newspaper |
|  Departmental/Center Newsletters |  Web-Based Clinical Trial Registries | |
|  YCCI Recruitment database |  Clinicaltrials.gov Registry (do not send materials to HIC) | |
|  Other (describe): | | |

3. Recruitment Procedures:

- a. Describe how potential subjects will be identified.
- b. Describe how potential subjects are contacted.
- c. Who is recruiting potential subjects?

Subjects will be recruited through flyers and advertisements in local newspapers, internet/web postings, through YCCI's recruitment systems: Epic's Enterprise electronic medical record (EMR), OnCore, Yale's clinical research management system (CRMS), and from community substance abuse treatment facilities. Subjects will participate in an initial phone screening and intake session to obtain informed consent with the research coordinator or research assistant, followed by physical examination and blood work to determine eligibility.

4. Screening Procedures

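### Hypothesis 2 predicts no drug effect at low withdrawal, but the plan gives no margin or interval rule that could support a claim of no effect

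*Combined protocol and SAP*

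**What the plan says.** All of this is in Section V, item 12 of the combined protocol and SAP.

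- **Specific Aim 2 and Hypothesis 2.** In high-withdrawal patients, prazosin is predicted to reduce heavy drinking days and any drinking days significantly against placebo. The second half of the hypothesis is: "No differences between medication treatment groups in the Low alcohol withdrawal individuals will be observed". No criterion is attached to it.
- **Power Analysis.** The design is a 2 x 2 of medication by alcohol withdrawal/anxiety, planned on d = .60, power .80 and p < .05. It concludes that "we would require 25 subjects per cell to adequately assess the proposed hypotheses for the clinical trial", a total of 100. It then adds: "Including a 15-20% drop-out after enrollment, we estimated recruitment of 120 AD patients into the trial".
- **Enrolment.** Section VII, Targeted Enrollment, gives "150 alcohol dependent men and women". The dosing table in Section V, item 3 shows 75 per arm.
- **Data Analytic Procedures.** Baseline withdrawal enters the main models as a mean-centred continuous CIWA-Ar score. A median split, with treatment contrasts in Low and High groups, is made only if an interaction with withdrawal is significant.

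**The concern.** A hypothesis of no difference needs a rule for what counts as support. A margin, an equivalence test or a confidence-interval criterion would do. None appears anywhere in the statistical section. What remains is a non-significant test in about half the sample, and such a test cannot tell no effect from an effect too small to detect at that size.

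At stake is what the trial may report about low-withdrawal patients. As worded, it could report that prazosin makes no difference to them when its data are compatible with a benefit close to the one it was designed to detect.

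**Working it through.** **Inputs.** d = .60, alpha .05 and power .80 come from the Power Analysis. Sidedness is not stated, so I take two-sided. Cell sizes are 25 (as stated), 120/4 = 30, and 150/4 = 37.5 (all enrolled patients analysed, even split).

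**The plan's own figure.** For two groups, n = 2(1.960 + 0.842)²/0.60² = 43.6, so 44 per group, or 45 with the t correction. For the main effect of drug, each arm spans two cells, so 22-23 per cell (N = 88-92) is enough. The plan's 25 per cell gives 84% power for that main effect. For a contrast inside one withdrawal stratum, 44-45 per cell would be needed, and 25 gives 55% power.

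**Low-withdrawal contrast taken alone.** Two-sample t-test with noncentrality d·√(n/2) on 2n − 2 df. The CI half-width is t(.975)·√(2/n).

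| Per cell | Noncentrality at d = .60 | Critical t | Missed, d = .60 | Missed, d = .40 | Missed, d = .30 | 95% CI half-width (SD) |
|---|---|---|---|---|---|---|
| 25 | 2.12 | 2.01 | 45% | 72% | 82% | 0.57 |
| 30 | 2.32 | 2.00 | 37% | 67% | 79% | 0.52 |
| 37.5 | 2.60 | 1.99 | 27% | 60% | 75% | 0.46 |

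One-sided, the d = .60 column becomes 33%, 26% and 18%.

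**With the gate applied.** I simulated 2 x 2 trials with pooled error on 4n − 4 df, SE √(2/n) for each stratum contrast and √(4/n) for the interaction. The split interaction stands in for the continuous model. The full pattern means: interaction significant in the predicted direction, High significant, Low not. Entries are for 25 / 30 / 37.5 per cell. The true effects are my assumptions.

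| True d, Low / High | Gate opens in predicted direction | Full pattern | Low non-significant, given that gate |
|---|---|---|---|
| .60 / .60 | 2.5% at each size | 2.4 / 2.3 / 2.3% | 97 / 95 / 90% |
| .30 / .90 | 32 / 37 / 45% | 31 / 36 / 42% | 98 / 97 / 94% |
| .60 / 1.20 | 32 / 37 / 45% | 25 / 24 / 22% | 77 / 66 / 49% |
| 0 / .60 | 32 / 37 / 45% | 27 / 32 / 40% | 93 / 93 / 94% |

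Compare the second and fourth rows. Once the gate has opened, a non-significant Low result is at least as likely when the true Low effect is .30 as when it is zero. It therefore cannot tell the two apart.

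**What a claim of no difference would need.** For a 95% interval to lie inside ±m with 80% power when the true difference is zero, n per arm in the low stratum is 2(1.960 + 1.282)²/m². That is 59 for m = .60 and 234 for m = .30. The plan has at most 37-38.

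**The case against.** The strongest reply is the gate. A reader might infer from the 27-45% miss rates that the plan would wrongly confirm Hypothesis 2 that often. The documents do not support that. Data Analytic Procedures analyses withdrawal as continuous and makes the Low and High contrasts only after a significant interaction. If prazosin works equally well in both strata, the false pattern is rare, at about 2.4%. This stands, and 27-45% describes the low-withdrawal contrast alone.

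The low figure does depend on reading the gate as Treatment by withdrawal. The text speaks of withdrawal as a moderator of Time and opens the split on any significant interaction with it. With no effective treatment gate, equal effects of .60 give High significant and Low not in about 19-24% of trials.

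Other parts of the reply also stand:

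- The documents never say that a non-significant Low test confirms the hypothesis. That is inferred from the lack of any other criterion.
- Specific Aim 2 is about high-withdrawal patients, and much of the remedy (continuous CIWA-Ar as moderator) is already planned.
- The t-test simplifies a mixed model with covariates, and there are two primary outcomes. Requiring both to be non-significant would lower the miss rate.

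A reader might also infer that a smaller trial confirms the hypothesis more readily. That is true only of the Low half read alone. The full pattern is flat across these sizes with equal effects, and rises with size at .30 / .90.

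Nor do the documents support saying that the result would decide who receives prazosin. The statement of purpose describes preliminary efficacy, and no rule restricts treatment.

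**Conclusion.** The concern holds, limited to the null half of Hypothesis 2. The plan predicts no difference at low withdrawal without a criterion that could support it, and 25 per cell is not adequate for that half. An estimate of exactly zero in the low stratum would still leave effects of about 0.46 to 0.57 SD inside the 95% interval.

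The gate protects well against a false claim of moderation when effects are equal, but it does not support a claim of no effect. A significant interaction says that the benefit is larger at higher withdrawal. In the .60 / .60 and .30 / .90 scenarios, a gate opened in the predicted direction is followed by a non-significant Low result in 90-98% of trials, so that result adds little. The proportion is lower (49-77%) only in the scenario with a High effect of 1.20.

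These figures assume one outcome, a two-sided 5% test, an even median split, no loss from the stated cell sizes, and effects in SD units. With 15-20% loss from 150, the cells fall to 150 × .85/4 = 31.9 or 150 × .80/4 = 30, close to the middle row of the first table.

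**What to change.** 1. Delete the sentence predicting no differences in low-withdrawal patients.
2. Restate Hypothesis 2 as one claim: the benefit of prazosin increases with baseline withdrawal. Test it by the Treatment by continuous CIWA-Ar term in the planned models, and name that term as the gate for any further contrasts.
3. From the same model, report the drug effect with its 95% interval at low and high CIWA-Ar scores fixed in advance.
4. Allow a statement of no worthwhile benefit at low withdrawal only if that interval lies inside a margin stated in advance and justified clinically.

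The cost is wording in Hypothesis 2 and the analysis section, with no extra patients or visits. The drawback is that a claim of no effect at low withdrawal will usually be unavailable. For the split contrast, a half-width of 0.46 SD cannot fit inside ±0.30 whatever the estimate, and fits inside ±0.60 only if the estimate is within 0.14 of zero. The continuous model does not escape this. With a linear interaction, the SE of the drug effect one SD below the mean score is √(4/N × (1 + 1)) = √(8/N), which equals √(2/n) for n = N/4, the same as for the split.
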